6.4 Unscheduled Visits

Unscheduled visits may occur if deemed clinically significant by the Investigator.

A patient will continue to be followed every 4 weeks (± 3 days) after their 56-day Follow-up Visit if their TTR protein levels continue to recover but have not returned to within 50% of Screening/Baseline visit levels. The patient will have the blood samples collected for the following clinical laboratory tests at these visits:

- Serum TTR protein and secondary PD biomarkers. Additionally, aliquots of serum samples will be taken and frozen, to permit testing of additional proteins related to ATTR.
- PK analysis

These patients will be followed until their TTR level returns to within at least 50% of the Baseline value.

7 STUDY ASSESSMENTS

7.1 Demographic Data and Medical History

Patient demographic data and a complete medical history will be obtained during Screening/Baseline. The medical history will also look to include prior neuropathy assessments, including but not limited to, Neuropathy Impairment Scales and Nerve Conduction Studies.

Any AEs from the previous study (ALN-TTR02-002) that are ongoing on Day 0 of Study ALN-TTR02-003 will be considered as part of the medical history and recorded on the Medical History case report form for the current study (ALN-TTR02-003).

7.2 Safety Assessments

All safety assessment measures will be recorded in the patient's medical record and CRF.

7.2.1 Physical Examination

Physical examinations will be performed by a physician and will include the examination of the following: general appearance, head, eyes, ears, nose, throat, chest/respiratory, heart/cardiovascular, gastrointestinal/liver, musculoskeletal/extremities, dermatological/skin, thyroid/neck, lymph nodes, and neurological/psychiatric.

Body weight will be measured at each study visit, with the exception of the 56-day Follow-up study visit, prior to dosing with ALN-TTR02. The weight measured during the previous dosing day should be used to calculate the dose of study drug. In the event that the weight obtained on the previous dosing day is not available, the weight obtained pre-dose on the dosing day can be used for dose calculation.

Height will only be measured at Screening/Baseline.

7.2.2 Vital Signs

Vital signs will be measured at Screening/Baseline and pre-dose at each subsequent study visit with the exception of the 56-day Follow-up visit; including systolic/diastolic blood pressure, pulse rate, respiratory rate, and oral body temperature. Vital signs will be measured in the supine position using an automated instrument after the patient has rested comfortably for 10 minutes. Each patient's blood pressure should be taken using the same arm. Oral temperature will be recorded in Celsius. Heart rate will be counted for a full minute and recorded in beats per minute. Respirations will be counted for a full minute and recorded in breaths per minute.

For the safety of the patient, additional vital signs may be added at the discretion of the Investigator.

7.2.3 Electrocardiogram

Computerized 12-lead ECG recordings will be obtained. Each lead shall be recorded for at least 3 beats at a speed of 25 mm/s. Triplicate recordings will be obtained during Screening/Baseline, approximately once every 6 months, at the 21-day Follow-up visit, and at the Early Termination visit.

The following electrophysiologic parameters will be assessed: rhythm, ventricular rate, PR interval, QRS duration, and QT interval. Either Bazett's and/or Fridericia's formula will be used to calculate the heart rate corrected QT interval (QTc).

For any clinically significant abnormal results, the Investigator must contact the CRO Medical Monitor to discuss continued participation of the patient in the study (e.g., ischemic ECG changes, wave/interval changes, or arrhythmia).

7.2.4 Ophthalmology Examination

Ophthalmology examinations will be performed at Screening/Baseline and approximately once every 6 months and at the Early Termination visit.

Further details regarding the ophthalmology examinations will be provided in the Study Reference Manual.

7.2.5 Clinical Laboratory Tests

Laboratory tests of hematology, serum chemistries, pregnancy (urine), coagulation studies, thyroid function tests, and urinalysis will be collected prior to the administration of premedications and dosing with ALN-TTR02 and will be performed by each study site's local laboratory.

In the event of an unexplained clinically relevant abnormal laboratory test occurring after study drug administration, the test should be repeated and followed up at the discretion of the Investigator until it has returned to the normal range or stabilized, and/or a diagnosis is made to adequately explain the abnormality.

The following clinical laboratory parameters are to be determined:

Hematology

- Hematocrit
- Hemoglobin
- Red blood cell (RBC) count
- White blood cell (WBC) count
- Mean corpuscular volume
- Mean corpuscular hemoglobin
- Mean corpuscular hemoglobin concentration
- Neutrophils, absolute and %
- Lymphocytes, absolute and %
- Monocytes, absolute and %
- Eosinophils, absolute and %
- Basophils, absolute and %
- Platelet count

Serum Chemistries

- Aspartate transaminase (AST)
- Alanine transaminase (ALT)
- Sodium
- Potassium
- Blood urea nitrogen (BUN)
- Creatinine
- Alkaline phosphatase
- Bilirubin (total and direct)
- Glucose
- Phosphate
- Albumin
- Calcium

Coagulation Studies

- Prothrombin time (PT)
- Activated partial thromboplastin time (aPTT)
- International Normalized Ratio (INR)

Thyroid Function Tests

- Thyroid stimulating hormone (TSH)
- Thyroxine (T4)
- Triiodothyronine (T3)

Urinalysis

- Visual inspection for color and appearance
- pH
- Specific gravity
- Ketones
- Protein
- Glucose
- Leukocytes
- Bilirubin
- Nitrite
- Urobilinogen
- Microscopic inspection of sediment

Other

- β -human chorionic gonadotropin (women of child-bearing potential only)

Additional and repeat testing may be performed at the discretion of the Investigator.

7.2.5.1 Hematology, Coagulation Studies, and Thyroid Function Tests

Blood samples for hematology, coagulation studies, and thyroid function tests will be collected Screening/Baseline, first dose, approximately every 6 months, at the 21-day Follow-up visit, and at the Early Termination visit. These samples are to be processed at the site's local laboratory.

7.2.5.2 Serum Chemistries and Urinalysis

Blood samples for serum chemistries and urine for urinalysis will be collected at Screening/Baseline, first dose, approximately every 3 months, at the 21-day Follow-up visit, and at the Early Termination visit. These samples are to be processed at the site's local laboratory.

7.2.5.3 Pregnancy Test

A urine pregnancy test will be performed for women of child-bearing potential at Screening/Baseline, and any time pregnancy is suspected, the results of which must be known prior to administration of study drug. Patients who are pregnant are not eligible for study participation. Patients determined to be pregnant while on study will be followed until pregnancy outcome is known (see [Section 8.12](#)).

7.3 Pharmacodynamic Assessments

Details of how samples will be collected, processed, and stored will be in the Study Laboratory Manual.

7.3.2 Secondary Pharmacodynamic Biomarkers

7.3.2.1 Retinol Binding Protein

Blood for serum RBP levels is to be collected at Screening/Baseline, immediately prior (within 10 minutes) to the administration of premedication and immediately prior (within 10 minutes) to first dose, and then approximately once every 3 months (prior to administration of premedications), at the 21- and 56-day Follow-up visits, and at the Early Termination visit. Select clinical assessments are to be performed on 2 separate days for each of the Mid-year and Annual study visits. For those visits, blood will be collected on each day that an assessment is performed.

In addition, for those patients enrolled in the PK/PD subgroup, blood for RBP levels will be collected prior to the administration of premedications at Month 8, and 24 hours, 3, 7, and 17 days post first dose and 8 and 24 month dosing days.

Serum RBP will be quantified using nephelometry.

7.3.2.2 Vitamin A

Blood for serum vitamin A levels is to be collected at Screening/Baseline, immediately prior (within 10 minutes) to the administration of premedication and immediately prior (within 10 minutes) to first dose, and then approximately once every 3 months (prior to administration of premedications), at the 21- and 56-day Follow-up visits, and at the Early Termination visit. Select clinical assessments are to be performed on 2 separate days for each of the Mid-year and Annual study visits. For those visits, blood will be collected on each day that an assessment is performed.

In addition, for those patients enrolled in the PK/PD subgroup, blood for vitamin A levels will be collected prior to the administration of premedications at Month 8, and 24 hours, 3, 7, and 17 days post first dose and 8 and 24 month dosing days.

7.4 Exploratory Biomarkers

To explore the expression of hepatocyte derived proteins to further characterize the biological effects of siRNA and/ or to explore possible metabolite profiling of ALN-TTR02, serum and plasma samples will be collected at selected time points (see Table 1-1).

Details of how samples will be collected, processed, and stored will be in the Study Laboratory Manual.

Biological samples for biomarker research and possible metabolic profiling can be retained on behalf of Alnylam for a maximum of 15 years following the last patient's last visit in the study.

7.5 Pharmacokinetic Evaluations

Details of sample collection and processing for PK analyses will be included in a laboratory manual.

7.5.1 Plasma Pharmacokinetics

The PK evaluation will include plasma-concentration time profiles for siRNA and the novel lipid components DLin-MC3-DMA and polyethylene glycol (PEG)₂₀₀₀-C-DMG. Details of the PK evaluation and analysis will be described in the PK and PK/PD analysis plan.

Plasma and urine samples will be evaluated using a validated ATTO-Probe-HPLC assay to determine siRNA concentration and by LC/MS/MS for DLin-MC3-DMA and PEG₂₀₀₀-C-DMG concentrations.

Blood sample collection times are included in the schedule of events (see Table 1-1 and Table 1-2 or Table 12-1 and Table 12-2). For all patients, plasma PK samples will be collected pre-dose (within 1 hour of planned dosing start) EOI and 1 hour post-dose at first dose and every dose up through, and including, the 3 month dosing visit, and then at 6, 9, and 12 month dosing days. Plasma PK samples will be collected pre-dose (within 1 hour of planned dosing start) and EOI at 15, 18, 21, and 24 month visits. The EOI will usually occur at 70 minutes after the start of the infusion, except in patients where the infusion has been prolonged. In addition, if the infusion is stopped and the site is considering restarting the infusion, a PK blood sample will be taken while the infusion is stopped. All PK samples will be collected according to the schedule of assessments when the dose is completed (i.e., all post-infusion times are relative to the EOI, regardless of the duration of the infusion). Plasma PK samples will also be collected at the Mid-year and Annual visits (1 sample collected on each of the 2 study visit days), the 21- and 56-day Follow-up visits, and the Early Termination visit.

For the PK/PD subgroup subjects, samples will be collected pre-dose, and at 1, 2, 4, 6, and 24 hours post-infusion; and at 3, 7 and 17 days post-dose for the first dose and the 8 and 24 month dosing days.

Pharmacokinetic analyses will consist of either a noncompartmental and/or compartmental analysis of plasma siRNA, DLin-MC3-DMA (lipid), and PEG₂₀₀₀-C-

DMG (lipid). Details of the PK evaluation and analysis will be described in the PK and PK/PD analysis plan. Pharmacokinetic parameter estimates to be calculated may include, but may not be limited to:

- Observed C_{max} .
- Time of observed maximum concentration (t_{max}).
- Partial area under the plasma concentration-time curve (AUC_p).
- Area under the plasma concentration-time curve to the last measurable concentration (AUC_{0-t}).
- Area under the plasma concentration-time curve from zero to the last measurable time point (AUC_{0-last}).
- Area under the plasma concentration-time curve extrapolated to infinity ($AUC_{0-\infty}$).
- Terminal elimination half-life ($t_{1/2\beta}$ and $t_{1/2\alpha}$).
- Elimination rate constant (λ_z).
- Systemic clearance (CL).
- Volume of distribution at steady state (V_{ss}).
- Volume of distribution based on the terminal phase (V_z).

Other parameters may be calculated if deemed necessary.

A population PK analysis of the siRNA will be performed by integrating the PK/PD subgroup and sparse samples collected during the study. Details of the Population PK evaluation and analysis will be described in the PK and PK/PD analysis plan. A compartmental model will be developed to model the concentration-time data of plasma siRNA and possibly DLin-MC3-DMA. Model evaluation and selection will be based on standard model diagnostics and goodness-of-fit criteria (e.g., log-likelihood difference) and by looking at pertinent graphical representations of goodness-of-fit (e.g., fitted and observed concentrations versus time, weighted residuals vs. time) to provide a robust evaluation of the population PK parameters of the siRNA and possibly DLin-MC3-DMA. Other parameters may be calculated if deemed necessary. Post hoc PK parameters of siRNA and possibly DLin-MC3-DMA will be derived with the population PK models and summarized using descriptive statistics.

As part of PK/PD analysis, additional PD baseline analysis on serum TTR, RBP, and vitamin A may be conducted to include the PD data obtained during PD recovery after receiving the last dose. Details of the PD evaluation and analysis will be described in the PK and PK/PD analysis plan. A PD analysis to determine PD parameters (e.g., 50% effective dose [ED_{50}], 50% effective concentration [EC_{50}]) will be conducted. The extent of suppression of TTR, RBP, and vitamin A (e.g., AUE, % E_{max} and E_{max}) will be evaluated using graphical display of data. Correlation between TTR versus RBP and vitamin A will also be performed (e.g., TTR concentrations, AUE, % E_{max} and E_{max} vs. RBP and vitamin A concentrations, AUE, % E_{max} and E_{max}). Whenever possible the strength of the relationship correlation will be evaluated using statistical estimators

(e.g. r^2 , slope, and p-value for a slope of 0). Other parameters may be calculated if deemed necessary.

The PK/PD analysis will include, but not be limited to, the determination of the relationship between exposure to siRNA, DLin-MC3-DMA and PEG₂₀₀₀-C-DMG (e.g., C_{max} and AUC) and the extent of suppression of TTR, RBP, and vitamin A (e.g., AUE, % E_{max} and E_{max}) will be explored using graphical display of data. Whenever possible the strength of the relationship correlation will be evaluated using statistical estimators (e.g. r^2 , slope, and p-value for a slope of 0). The PD and PK/PD parameters will include, but not limited to, descriptive statistics (e.g., mean, standard deviation, coefficient of variation, median, minimum, maximum, geometric mean, and geometric CV%) and also by statistical comparisons whenever possible. Other parameters may be calculated if deemed necessary. Details of the PK evaluation and analysis will be described in the PK and PK/PD analysis plan.

7.5.2 Urine Pharmacokinetics

The CL_R of siRNA and 4-dimethylaminobutyric acid (metabolite of DLin-MC3-DMA) after dosing with ALN-TTR02 will be evaluated for the subjects in the PK/PD subgroups and whenever possible for other subjects in the study. Other parameters may be calculated if deemed necessary. Details of the urine PK evaluation and analysis will be described in the PK and PK/PD analysis plan. Urine sample collection times are included in the schedule of assessments (see Table 1-1 and Table 1-2 or Table 12-1 and Table 12-2).

Urine will be collected into suitable containers and kept refrigerated.

7.6 Clinical Activity Assessments

Assessment of clinical activity will occur approximately every 6 months. Additional and repeat testing may be performed at the discretion of the Investigator and in conjunction with the Sponsor.

Further details on performing these assessments will be provided in the Study Reference Manual.

7.6.1 Modified Neurological Impairment Score (mNIS) + 7

The mNIS + 7 assessment includes the modified NIS tool (weakness and reflexes only), nerve conduction studies (NCS), quantitative sensory testing (QST) by body surface area including touch pressure (TP) and heat pain (HP), and postural blood pressure.

At each time point, 2 independent assessments will be performed. Each site will make every effort to have these assessments performed by the same Investigator. Assessments are to be performed at least 24 hours (approximately) apart from each other but not more than 7 days apart. In order to limit potential intra-operator bias, results of the first assessment will not be available to the Investigator when performing the second assessment.

Every effort will be made to use the same device for NCS and QST for a patient throughout the duration of the study.

7.6.2 Vibration Detection Threshold

Large nerve fiber function will be further evaluated by VDT using the Computer Aided Sensory Evaluator, version IV. Tests are automated and will last approximately 3 minutes.

At each time point, 2 independent assessments will be performed. Each site will make every effort to have these assessments performed by the same Investigator. Assessments are to be performed at least 24 hours (approximately) apart from each other but not more than 7 days apart. In order to limit potential intra-operator bias, results of the first assessment will not be available to the Investigator when performing the second assessment.

Every effort will be made to use the same device for a patient throughout the duration of the study.

7.6.3 Heart Rate Response to Deep Breathing

The HRdb test evaluates autonomic function by the cardio-vagal response. The average heart rate difference while taking eight deep breaths is measured.

At each time point, 2 independent assessments will be performed. Each site will make every effort to have these assessments performed by the same Investigator. Assessments are to be performed at least 24 hours (approximately) apart from each other but not more than 7 days apart. In order to limit potential intra-operator bias, results of the first assessment will not be available to the Investigator when performing the second assessment.

Every effort will be made to use the same device for a patient throughout the duration of the study.

7.6.4 Hand Grip Strength

Hand grip strength will be measured by dynamometer. When performing the test, patients will stand, holding the dynamometer in their dominant hand, with their arm parallel to the body without squeezing the arm against the body. Tests will be performed in triplicate on the same day at each time point.

At each time point, 2 independent assessments (each assessment performed in triplicate) will be performed. Assessments are to be performed at least 24 hours (approximately) apart from each other but not more than 7 days apart.

Every effort will be made to use the same dynamometer for a patient throughout the duration of the study.

7.6.5 Ten-meter Walk Test

Patients will have to be able to walk without assistance for 10 meters in order to complete the 10-meter walk test. The time required for the patient to complete 2, 8, and 10 meters will be recorded. This will allow for any potential variation due to acceleration and deceleration. The patient will complete 1 trial.

At each time point, 2 independent assessments will be performed. Assessments are to be performed at least 24 hours (approximately) apart from each other but not more than 7 days apart.

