9.2.6 Summary of Clinical Activity Assessments

Summary statistics of observed values and changes from baseline will be provided for the mNIS +7 composite score. Summaries will also be provided for the components of the composite score (i.e., the NIS weakness and reflex scores, the Σ5 NC, and QST values). The full NIS (i.e., the sum of cranial nerve, muscle weakness, reflex and sensation scores) will be summarized also. Values of the individual components of the mNIS weakness and reflex scores will be depicted graphically by presenting the mean (±SE) values over time for each location (hip, knee, etc.).

Patient reported quality of life and disease burden will be assessed by summary statistics for the EQ5D and R-ODS. Summary statistics will be provided for observed values and changes from baseline. Patient reported autonomic neuropathy symptoms will be assessed by descriptive statistics for the COMPASS 31.

Descriptive statistics will also be provided for observed values and changes from baseline in motor function (10-meter walk test and test of grip strength), nutritional status (mBMI), sensory and autonomic innervation (IENFD and SGNFD), VDT, and ambulation (FAP stage and PND score).

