3.4. Baseline Definitions

Unless otherwise noted, baseline will be defined as the study ALN-TTR02-003 Day 1 pre-dose value when non-missing, otherwise the latest value from amongst any screening or unscheduled assessments prior to dosing on Day 1 will be used (i.e., the measurement closest to and prior to dosing will be considered baseline). For PD parameters (TTR, RBP, vitamin A), baseline will be defined as the average of all records, including those from any unscheduled visits, prior to the date and time of first dose. For the mNIS+7/NIS+7 total score and individual components, grip test and 10m walk test, baseline is defined as the average of the Screening/Baseline assessments.

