3.9. Missing, Unused, and Spurious Data

Specific algorithms will be used impute values and/or subcomponents of particular clinical activity assessments when subcomponents are missing (mNIS+7, NIS+7, EQ-5D, R-ODS, and

COMPASS; see Sections 7.1-7.4). In general, there will be no imputation for missing data for other endpoints unless specified otherwise. All data recorded on the CRF will be included in data listings that will accompany the CSR.

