4.4. Summary of Clinical Activity Assessments

The following clinical activity assessments will be collected:

- Neurologic impairment will be assessed using the mNIS + 7 composite score, consisting of the NIS weakness and reflex domains, 5 nerve conduction studies (Σ 5 NCS), quantitative sensory testing (QST) by body surface area including touch pressure (TP) and heat pain (HP), as well as autonomic assessment through postural blood pressure. A scoring algorithm, including methods for handling missing components of the mNIS+7, is included in Section 7.1.
- The NIS score (i.e., the sum of cranial nerve, muscle weakness, reflex and sensation scores) will also be assessed.
- Neurologic impairment will also be assessed by NIS+7 [19]. The NIS+7 includes the full NIS, sum of five NCS (overlapping but not identical to the Σ 5 NCS calculated for mNIS+7 above, vibration detection threshold [VDT], and heart rate response to deep breathing [HRdb]). A scoring algorithm for the NIS+7 is included in Section 7.1.
- Patient reported QOL will be evaluated using the EQ-5D index value (using U.S. references to calculate the index). Categorical summaries of each EQ-5D domain will be provided. Overall health will be assessed by the EQ-VAS. Disability will be reported by patients using the R-ODS. Scoring algorithms for the EQ-5D and R-ODS are included in Section 7.2 and Section 7.3.
- Motor function assessments will include a timed 10-meter walk test and test of grip strength in dominant arm, as well as an evaluation of ambulation using PND score and FAP stage.
- Pathologic evaluation of sensory and autonomic innervation will be evaluated by IENFD analysis and quantitation of SGNFD via tandem 3 mm skin punch biopsies taken from the leg and thigh.
- Nutritional status of patients will be evaluated using the mBMI, calculated as BMI (kg/m^2) multiplied by albumin (g/L).

- To evaluate patient reported autonomic neuropathy symptoms, patients will complete the COMPASS 31 questionnaire, consisting of 31 clinically selected questions which evaluate 6 autonomic domains [1]. A scoring algorithm for the COMPASS-31 total score and domain scores is included in Section 7.4.
- Magnetic resonance neurography (MRN) of peripheral nerves in the lower extremity and lumbar plexus will be performed for consenting patients.

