Analyses of clinical activity assessments will use the Full Analysis Set. Summary statistics of observed values and changes from baseline will be provided for the mNIS+7 composite score. Summaries will also be provided for the components of the composite score (i.e., the NIS weakness and reflex scores, the Σ 5 NCS, QST values, and postural blood pressure). The full NIS (i.e., the sum of cranial nerve, muscle weakness, reflex and sensation scores) and NIS+7 will also be summarized overall and by component as above.

Patient reported autonomic neuropathy symptoms will be assessed by descriptive statistics for the COMPASS 31 (including overall and domain scores).

Descriptive statistics will also be provided for observed values and changes from baseline in motor function (10-meter walk test speed and grip strength), nutritional status (mBMI), sensory and autonomic innervation (IENFD and SGNFD), and ambulation (FAP stage and PND score).

The above clinical activity parameters will be summarized overall, by stabilizer use (any versus none), and by Cardiac Subgroup versus all others. The mNIS+7 composite score and component scores will also be summarized by baseline age (<65 vs \geq 65) and gender.

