7. QUESTIONNAIRE/SCORING APPENDICES

In questionnaires, if multiple responses are provided to a single-response question, the question is deemed as missing.

7.1. Modified Neuropathy Impairment Score (mNIS+7) and Original Neuropathy Impairment Score + 7 Nerve Tests (NIS+7)

Note: the mNIS+7 and NIS+7 measurements are conducted in duplicate per timepoint. The average of two complete duplicate values will be reported, except in cases of missing or partially missing data as described below.

Assessment Tool	Total Points	Components (maximum points)
Modified NIS+7	304	
 • NIS-W: Weakness (192) • NIS-R: Reflexes (20) • Quantitative sensory testing by body surface area including touch pressure (TP) and heat as pain (HP): QST-BSA_{TP+HP5} (80) • $\sum 5$ nerve conduction studies (10) 
 • Ulnar compound muscle action potential (ulnar CMAP) • Ulnar sensory nerve action potential (ulnar SNAP) • Sural sensory nerve action potential (sural SNAP) • Tibial compound muscle action potential (tibial CMAP) • Peroneal compound muscle action potential (peroneal CMAP) • Postural blood pressure (BP) (2)
NIS+7	270	
 • NIS-W: Weakness (192) • NIS-R: Reflexes (20) • NIS-S: Sensation (32) • $\sum 7$ Nerve tests 
 • 5 Nerve conduction studies $\sum 5$ (18.6) 
 • Peroneal compound muscle action potential (peroneal CMAP) • Peroneal motor nerve conduction velocity (peroneal MNCV) • Peroneal motor nerve distal latency (peroneal MNDL) • Tibial motor DL • Sural sensory nerve action potential (sural SNAP) • Vibration detection threshold (VDT) (3.72) • Heart rate response to deep breathing (HRdb) (3.72)

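### Walk-speed summaries appear to drop patients who can no longer walk 10 m unassisted, so they describe only those still walking

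*Protocol*

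**What the plan says.** The walk test serves a secondary objective (Protocol 2.2, SAP 1.1.2.2). Four parts of the plan bear on a patient who cannot do it.

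- **Who can complete it.** Protocol 7.6.5: "Patients will have to be able to walk without assistance for 10 meters in order to complete the 10-meter walk test". Times to 2, 8 and 10 m are recorded. No value or code for inability is described. The footnote to the SAP's Year 1 schedule repeats the condition.
- **What is summarised.** Protocol 9.2.6 plans descriptive statistics for "observed values and changes from baseline in motor function (10-meter walk test and test of grip strength". SAP 4.4 names the variable as a speed, "motor function (10-meter walk test speed and grip strength", and uses the Full Analysis Set. SAP 3.2 gives n, mean, median, SD, minimum and maximum for continuous variables. A category for missing data is planned for categorical variables only.
- **Missing data.** SAP 3.9 provides algorithms for mNIS+7, NIS+7, EQ-5D, R-ODS and COMPASS. For the rest: "In general, there will be no imputation for missing data for other endpoints unless specified otherwise". I found nothing specified for the walk test in the visible text.
- **Other information on walking.** SAP 4.4 lists the walk test and grip strength "as well as an evaluation of ambulation using PND score and FAP stage".

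**The concern.** A patient who loses unassisted walking has no 10 m time, so no speed and no change score. The value is absent because of the decline that the test is meant to measure. The visit summary then covers the remaining walkers, and n falls without a stated reason.

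The same SAP treats inability differently elsewhere. R-ODS gives 0 to an activity that the patient cannot perform (SAP 7.3), and the worst EQ-5D level covers being unable (SAP 7.2). The walk test has no counterpart.

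At stake is a misread secondary result. The study has one arm, so there is no control group with the same omission to compare against. SAP 4.4 also splits the summaries by stabilizer use and by Cardiac Subgroup, where each lost patient weighs more because n is smaller.

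**Working it through.** The plan states no walk speed, SD, target difference or rate of lost walking, and the sample size is not based on power (SAP 3.1). There is no figure of the plan's own to reproduce. The arithmetic below only shows how the size depends on quantities that the documents do not give.

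**Inputs.** N = 28 is the enrolment ceiling (Protocol 9.1, SAP 3.1), taken here as all able to walk at baseline. Assumed: k patients lose walking, their mean baseline speed is b, and the other N − k change by d on average. No other tests are missing.

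**Formulas.**

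- Observed-case mean change = d
- Mean change with inability scored 0 m/s = [(28 − k)d − kb]/28
- Gap (observed minus zero-scored) = k(b + d)/28

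**Results (m/s).**

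| k | b | d | Observed | Zero-scored | Gap |
|---|---|---|---|---|---|
| 0 | any | 0 | 0.000 | 0.000 | 0.000 |
| 1 | 0.4 | 0 | 0.000 | −0.014 | 0.014 |
| 1 | 0.8 | 0 | 0.000 | −0.029 | 0.029 |
| 3 | 0.6 | 0 | 0.000 | −0.064 | 0.064 |
| 3 | 0.6 | −0.1 | −0.100 | −0.154 | 0.054 |
| 3 | 0.6 | +0.05 | +0.050 | −0.020 | 0.070 |
| 3 | 0.6 | +0.1 | +0.100 | +0.025 | 0.075 |
| 3 | 0.6 | −0.6 | −0.600 | −0.600 | 0.000 |
| 3 | 0.6 | −0.7 | −0.700 | −0.689 | −0.011 |
| 5 | 0.8 | +0.1 | +0.100 | −0.061 | 0.161 |

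Worked example, fourth row: (25 × 0 − 3 × 0.6)/28 = −1.8/28 = −0.064. In the sixth row the sign of the reported change differs between the two summaries. The gap vanishes at d = −b and reverses below it. Over k = 0 to 5, b = 0.4 to 0.8 and d = −0.1 to +0.1, it runs from 0 to 0.161.

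**Recovery works the other way.** A patient unable at baseline who later walks at 0.6 m/s has no observed change score. With the other 27 stable, the observed change is 0.000 and the zero-scored change is 0.6/28 = +0.021. If three lose walking at 0.6, one regains 0.6 and 24 are stable, the zero-scored change is (−1.8 + 0.6)/28 = −0.043 against an observed 0.000.

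**The observed visit mean can move too.** Suppose 25 patients walk at a steady 1.0 m/s and three walk at 0.6 before losing the ability. The mean goes from (25 × 1.0 + 3 × 0.6)/28 = 0.957 at baseline to 1.000, a rise of 0.043 with nobody walking faster.

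**The case against.** **Exclusion is inferred.** Protocol 7.6.5 governs completing the test, not scoring it. SAP 3.9 is hedged, and the documents give no derivation of speed from the recorded times. Protocol 7.6 adds: "Further details on performing these assessments will be provided in the Study Reference Manual". That manual and the CRF are not available here and may hold some of the detail. This stands, and is why the heading says the summaries appear to drop these patients. An analysis rule would still belong in the SAP.

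**Direction needs a reference.** A reader might infer that the walk result is simply biased toward benefit. The documents do not support that. As a description of those who completed the test, with n shown, the observed mean is correct. It is too favourable only relative to a stated convention such as 0 m/s, only if patients lose walking, and only while d is above −b.

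**Loss of ambulation is reported elsewhere.** PND score and FAP stage are summarised, and all data are listed by subject. These can show that walking was lost, but they leave the walk-speed mean and change as they were.

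**No evidence that it happens.** Protocol 1.6.1 reports stable neuropathy scores through 12 months. A reader might take the Karnofsky floor of 60%, the lack of a walking criterion, or baseline PND categories up to IV (SAP 4.2) as proof that some patients cannot walk 10 m. These show only that such patients are not ruled out.

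**Low stakes.** The primary objective is safety, and no hypothesis is tested. That limits the harm to interpretation.

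**Related small gaps.** Unassisted walking is not defined with respect to walking aids, and a definition added to the SAP could not change tests already done. Two assessments are made per time point, but for the "grip test and 10m walk test, baseline is defined as the average of the Screening/Baseline assessments"; no such rule is given after baseline, and the duplicate rule in SAP 7.1 says only that "the mNIS+7 and NIS+7 measurements are conducted in duplicate per timepoint". On assumed values, counting a patient who walks 0.6 once and is unable once as 0.6 or 0.3 moves the group mean by 0.3/28 = 0.011. These are minor missing details and do not carry the point.

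**Conclusion.** The point holds as a consequence of the rules read together: walk speed and its change at each visit appear to describe only patients still able to walk 10 m unassisted. Against the 0 m/s convention the observed change is too favourable by k(b + d)/28, which is 0.064 m/s for the assumed k = 3, b = 0.6, d = 0. The true size is unknown and may be zero, since every value of k, b and d is an assumption, and recoveries would offset it. The consequence is a secondary descriptive result that could be misread, not a false test. It is worth correcting because the plan's other ambulation measures can signal the problem but do not repair this summary.

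**What to change.** In SAP 3.9 and 4.4:

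1. Keep the observed-case summary as planned.
2. Beside it, at every visit including baseline, give the number and percentage unable to complete the walk test for disease-related reasons. Count tests of unknown reason separately.
3. Add one supplementary summary that scores disease-related inability as 0 m/s at any visit including baseline, labelled as a convention.
4. Leave tests missing for other or unknown reasons as missing.
5. Take the reason from the record, or query missing tests where none was recorded.

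**Cost.** SAP wording and one extra summary. Queries concern missing tests only. Their ceiling is 28 × 5 = 140 patient time points (baseline, 6, 12, 18 and 24 months), or 280 assessments at two per time point.

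**Downside.** 0 m/s is not a true speed for someone who walks with help, so the supplementary summary must be read with the count unable. Reasons collected in retrospect may be incomplete, and the result may look slightly less favourable.
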